3.2. Unblinded / non-randomized sentinel groups

As safety precaution, the study will begin with the enrolment of a small group of sentinel subjects (“Sentinel Groups”), each of whom will receive the vaccine in an unblinded and non-randomized manner. The investigator, the pharmacist and site personnel performing study related assessments, all participants of the “Sentinel Groups”, as well as the sponsor’s representatives involved in the monitoring and conduct of the study will be unblinded. The enrolment of the “Sentinel Groups” will be conducted in one investigational site. The one located in the country where approval and authorization from Ethics Committee and Competent Authority will be obtained first.

Six sentinel subjects will be enrolled either in Cohort A (low dosage, vaccinations on days 0 and 28) or in cohort B (high dosage, vaccinations on day 0 and 28) according to the following scheme:

- The first subject of the “Sentinel Groups” will be enrolled in cohort A and will receive the low dose vaccine on day 0.
- Twenty-four hours after the injection, the subject will be called to collect safety information related to the vaccination.
- The clinical investigator can then decide to move on with the vaccination of the second and third subject based on the absence of related severe AEs/SAEs (no less than 24hrs after the first subject received the first treatment and phone call).
- The second and third subject of the “Sentinel Groups” will be enrolled, the same day with an interval of at least 3 hours, in cohort A and will receive the low dose vaccine on day 0.
- Twenty-four hours after the injection, the second and third subject will be called to collect safety information related to the vaccination.
- The clinical investigator can then decide to move on with the vaccination of the fourth subject based on the absence of related severe AEs/SAEs (no less than 24hrs after the second and third subject received the first treatment and phone call).
- The fourth subject of the “Sentinel Groups” will be enrolled in cohort B and will receive the high dose vaccine.
- Twenty-four hours after the injection, the subject will be called to collect safety information related to the vaccination.

- The clinical investigator can then decide to move on with the vaccination of the two last subjects based on the absence of related severe AEs /SAEs (no less than 24hrs after the fourth subject received the first treatment and phone call).
- The fifth and sixth participants of the “Sentinel Groups” will be enrolled, the same day with an interval of at least 3 hours, in cohort B and will receive the high dose vaccine on day 0. 24 hours after the injection, they will be called to collect safety information related to the vaccination.
- Following the 14 day follow up of all sentinel subjects, the DSMB will review safety data after the first dose in these six participants, before giving a positive written recommendation for continuing with the double-blind, randomized treatment phase.

Following the 42-day follow-up of all sentinel subject, a medical monitoring of safety data will be performed to evaluate safety of the second injection in these six participants. In case of any safety concern, an ad hoc DSMB meeting will be organized before giving a positive recommendation for continuing with the second injection of the double-blind, randomized cohorts (“main cohorts”). In case of any related severe AE or related SAE, Sponsor will be contacted and after the case has been discussed by the Sponsor and DSMB it will be determined if study vaccine can be continued according to the protocol.

All subjects included in the “Sentinel Groups” will be included in the shedding assessment. Body fluids including saliva, nasal swab, urine and whole blood will be collected therefore at visit 1 (day 0), visit 2 (day 7), visit 3 (day 14), visit 4 (day 28) and visit 5 (day 42).

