As a correlate of protection is not yet known, it is unclear at this time which magnitude of the immune response, and in particular of which parameter, will be required. Thus, different parameters of the immune response, particularly neutralizing antibodies and T cell responses will be followed. In case a correlate of protection becomes available during the study, the efficacy of the different regimen will be evaluated based on the established correlate.

This study will address the immune response to COVID-19 vaccine on days 28 and 56 as well as the long-term durability of specific anti-SARS-CoV-2 antibody response up to day 91 after administration of two different dose levels.

A Virus Neutralizing Test (VNT) will be used to analyze functional anti-SARS-CoV-2 antibodies induced by COVID-19 vaccine throughout the entire study.

The induction of virus specific T-cells is known as a critical step in the generation of a functional immune response. For this purpose, the rate of SARS-CoV-2 virus-specific T cells will be determined for all timepoints of the study.

Additionally, Enzyme-linked immunosorbent assays (ELISAs) will be performed to obtain data on SARS-CoV-2 antibody (Ab) titer of all treatment groups starting with baseline up to D91, as well as on the development of measles antibody titer up to day 56 after the first treatment.

As mentioned before, a staggered unblinded dose-escalation design has been implemented to ensure careful observation on subjects' safety during the first treatments. In the unblinded dose-escalation phase the study safety data will be available for a subset of three sentinel subjects per dose level, 14 days following the first vaccinations in order to initiate the blinded randomization part of the study. Only after written favorable opinion of the DSMB, randomization to the blinded treatment phase will be initiated. Subjects will be followed closely by the investigators of both study sites. Individual as well as treatment halting rules have been implemented for safety monitoring.

In the Phase I study, healthy subjects 18-55 years of age will be enrolled which is a typical age group for a First-in-Human trial with the primary objective to confirm safety. Older age groups, who are most affected by COVID-19, are planned to be included in the advanced clinical trials.

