3.3. Blinded / randomized cohorts

After DSMB review and positive recommendation, sponsor will decide to continue the study by the enrollment of the remaining 84 participants (“Main Cohorts”), in a blinded randomized manner, in the low dose group (cohort A) or in high dose groups (cohort B and C).

Table 1: Treatment groups allocation

| Cohort | Treatment | Injection 1 D0 | Injection 2 D28 | Number of participants | | |
|--------|----------------------|-------------------|--------------------|------------------------------|------------------------------|---------|
| | | | | COVID-19 vaccine Sentinel | COVID-19 vaccine Main grp | Placebo |
| A | COVID-19 low Dosage | Vaccine | Vaccine | 3 | 21 | 6 |
| B | COVID-19 high Dosage | Vaccine | Vaccine | 3 | 21 | 6 |
| C | COVID-19 high Dosage | Vaccine | Placebo | 0 | 24 | 6 |

Participants will be observed closely for safety and immunogenicity from the first injection to the end of study.

The investigator, and site personnel performing study related assessments, all participants, as well as the sponsor’s representatives involved in the monitoring and conduct of the study will be blinded.

Only site personnel performing randomization, preparation of IMP and monitoring of the IMP handling process will be unblinded as well as the DSMB members (excluding observing DSMB members who will only have access to blinded safety report).

During the follow up phase (after all subjects have completed V6), the head of vaccine programs of Institut Pasteur and a project manager from the vaccine developer (Themis Bioscience GmbH a subsidiary of Merck & Co., Inc., Kenilworth, New Jersey USA,) will have access to the unblinded data for the purpose of immunogenicity assessment. In the current pandemic, rapid assessment of the potential of the vaccine, including the balance of safety and immunogenicity is required to move promising candidates forward as quickly as possible. All data will be stored on a secured server accessible with a login and password to which only the unblinded person has access. The risk of impact on the study is minimized as unblinding will occur when the treatment phase will have been completed, the analyses have been defined, and the unblinded personnel is not involved in the clinical evaluation and management of the participants.

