7.2.6. Visit 4 - Second injection (Day 28±3)

This visit will take place 28±3 days after the first vaccination. Participants will be interviewed by a physician, or his/her delegate, of the investigational clinical site about any changes in their medical status, concomitant medications and/or occurrence of any AEs, AESI an SAE since the last visit.

The following assessment / activities will be performed during this visit and before the second injection

- Check if participant has met any individual halting rule
- Record of demographics (*only weight and BMI*).
- A directed physical examination.
- Record of vital signs in sitting or supine position*.
- Safety laboratory evaluations (blood and urine).
- Urine pregnancy test (For Females).
- Breath alcohol and urine drug tests (as outlined in Appendix 1)
- A blood sample will be drawn for immunomonitoring analysis.
- Saliva, Urine, nasal swab and an additional blood sample will be collected/drawn in the “Sentinel Groups” for shedding assessment.

* *Vital signs can be measured in sitting or supine position as well as long as within 1 patient the measurements are always done in the same position*

During the visit, the Investigator may order one re-test of the following parameters: demographics (Weight and BMI), vital signs (HR, RR, BP, body temperature), safety laboratory tests, urine pregnancy test (for females), breath alcohol and/or urine drug tests, if they need to evaluate the evolution of that parameter(s) or to confirm the value observed. Results of this re-test must be available prior to the second administration of the investigational product. The reason and results of this re-test will be documented in the participant's source data and in the eCRF.

If, no significant change in the participant's health since the last visit, he/she will receive the second intramuscular injection into the deltoid muscle of the opposite arm of the first injection ideally. The time and the arm (left or right) in which the vaccine was injected will be recorded in the participant's source data and in the eCRF.

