7.2.8. Visit 5 - Follow-up 2 (Day 42±3)

This visit will take place 42±3 days after the first injection. Participants will be interviewed by a physician, or his/her delegate, of the investigational clinical site about any changes in their medical status, concomitant medications and/or occurrence of AEs, AESI and SAE since the last contact. Diaries will be collected, reviewed and all AEs will be documented in participant's source data and in the CRFs.

The following assessment / activities will be performed during this visit

- Check if participant has met any individual halting rule
- Examination of the site of injection and assessment of local reaction.
- Record of vital signs in sitting or supine position*.
- A blood sample will be drawn for immunomonitoring analysis

* *Vital signs can be measured in sitting or supine position as well as long as within 1 patient the measurements are always done in the same position.*

During the visit, the Investigator may order one re-test of the following parameters: vital signs (HR, RR, BP, body temperature), if they need to evaluate the evolution of that parameter(s) or to confirm the value observed. The reason and results of this re-test will be documented in the participant's source data and in the eCRF

Saliva, Urine, nasal swab and an additional blood sample will be collected/drawn in the “Sentinel Groups” for shedding assessment.

At the end of the visit, the next visit (Visit 6) will be scheduled and confirmed.

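### The visit calendar does not secure that the sentinel Day 42 safety review comes before the first main-cohort second injections, and Visit 5 is not tied to injection 2

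*Protocol*

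**What the plan says.** The protocol describes two safety steps based on the six sentinels.

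The first opens the main cohorts. Section 3.2: "Following the 14 day follow up of all sentinel subjects, the DSMB will review safety data after the first dose in these six participants". Section 1.4 makes the order explicit: "Only after written favorable opinion of the DSMB, randomization to the blinded treatment phase will be initiated". Section 3.3 adds a sponsor step: "After DSMB review and positive recommendation, sponsor will decide to continue the study by the enrollment of the remaining 84 participants".

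The second concerns the repeat dose. Section 3.2: "Following the 42-day follow-up of all sentinel subject, a medical monitoring of safety data will be performed to evaluate safety of the second injection". For the case that this review raises a safety concern, the same section provides: "an ad hoc DSMB meeting will be organized before giving a positive recommendation for continuing with the second injection of the double-blind, randomized cohorts". Synopsis item 17 (DSMB) and section 4.12 say the same and call this review Intermediate Report 2 (IR2).

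On timing, section 7.2.6 says of Visit 4: "This visit will take place 28±3 days after the first vaccination". Section 7.2.8 says of Visit 5: "This visit will take place 42±3 days after the first injection". Visit 3 is at Day 14 ± 1 (7.2.5). Synopsis item 17 nevertheless describes Visit 5 as lying 14 days after injection 2.

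**The concern.** All three descriptions of the second step place it ahead of continuing second injections in the main cohorts. For the first step the protocol says outright that randomization waits. For the second it gives no equivalent statement, no minimum interval between the sentinels and the main cohorts, no duration for either review and no provision for a late review. The only grounds that section 7.2.6 names for giving injection 2 later are acute illness and fever.

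A site could therefore follow the schedule exactly and give the first main-cohort second injections before the sentinel second-dose data have been reviewed. For those subjects a review meant to look ahead would look back, in a first-in-human trial of a live vector.

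The Visit 5 timing adds to this. IR2 is prepared once the sentinels complete Visit 5, and the second diary is retrieved there. If Visit 5 comes early relative to injection 2, the diary and the review cover less than the 14-day solicited period named in the primary outcome (section 2.2.1).

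**Working it through.** The protocol gives no figure of its own for the interval between the two steps, so there is none to reproduce. What follows is calendar arithmetic.

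**Inputs**
- T: day of the last sentinel's first injection. Both steps wait for all six sentinels, so both are counted from T.
- Visit 3: 14 ± 1 days (7.2.5). Visit 4: 28 ± 3 days (7.2.6). Visit 5: 42 ± 3 days (7.2.8). All are counted from the first injection.
- L: days from completion of the last sentinel's Visit 3 to the first main-cohort injection. It covers DSMB review, written recommendation, sponsor decision and enrolment. Not stated; L ≥ 0.
- R: days from the last sentinel's Visit 5 to completion of the review. Not stated; R ≥ 0.

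**Formulas**, with w3, w4 and w5 the deviations of the visits from nominal:
- First main-cohort second injection = T + (14 + w3) + L + (28 + w4)
- Review complete = T + (42 + w5) + R
- Lead of injection over review = w5 − w3 − w4 + R − L

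**Nominal visits:** 14 + 28 = 42, so the lead is R − L.

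**Window limits** (sentinel Visit 3 at −1, main Visit 4 at −3, sentinel Visit 5 at +3): injection at T + 13 + L + 25 = T + 38 + L; review complete at T + 45 + R. The lead is 7 + R − L.

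Lead in days over a range of assumed L and R (positive means the injection comes first):

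| L | R | Nominal | Largest |
|---|---|---|---|
| 0 | 0 | 0 | 7 |
| 0 | 7 | 7 | 14 |
| 3 | 0 | −3 | 4 |
| 3 | 3 | 0 | 7 |
| 7 | 0 | −7 | 0 |
| 7 | 3 | −4 | 3 |
| 10 | 0 | −10 | −3 |
| 10 | 7 | −3 | 4 |
| 14 | 7 | −7 | 0 |

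With R = 0, reversal is possible for L below 7 days, the worst case is same-day at L = 7, and reversal is impossible above 7. With L = R, the two fall on the same day at nominal visits and can reverse by up to 7 days.

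**Who is affected.** From Table 1 (section 3.3), 21 + 21 = 42 of the 84 main-cohort subjects are allocated vaccine at Day 28. The other 24 + 6 + 6 + 6 = 42 receive saline. Inclusion is planned over about 6 weeks (8.6), so only the earliest-enrolled can be reached.

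**Visit 5 relative to injection 2** (no assumption needed):
- Shortest: (42 − 3) − (28 + 3) = 39 − 31 = 8 days
- Longest: (42 + 3) − (28 − 3) = 45 − 25 = 20 days

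At 8 days, 14 − 8 = 6 days of the solicited period are still to come when the diary is retrieved.

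**The case against.** The strongest reply is that L cannot be zero. A DSMB review, a written opinion, a sponsor decision and enrolment all come first, and each day they take moves the first second injection a day later. IR2 covers six open-label subjects without a database lock, so R may be short. The 7-day figure needs three windows at their extremes at once, and a window permits an early injection without requiring one. All of this stands. It shows that the intended order may well be met in practice, but nothing in the protocol ensures it.

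A reader might infer that the review is the only protection against second-dose harm. The documents do not support that. The study halting rules (4.9.1) apply to further administration, sentinels are telephoned 24 hours after injection 2 (7.2.7), and unscheduled DSMB meetings are possible at any time (4.12). Because sentinel treatment is open, an event after their second dose can prompt action before Day 42. Nor are 84 subjects exposed to an unreviewed second vaccine dose: half receive saline at Day 28.

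The absence of a review check from the Visit 4 list is weak evidence. The Visit 1 list likewise omits the mandatory first DSMB clearance, so study-level steps evidently sit elsewhere. The point therefore rests on sections 3.2 and 4.12 and synopsis item 17. Convening the DSMB only on a safety concern is a choice stated consistently in all three, and it is not challenged here.

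On Visit 5, the 14 ± 1 day diary retrieved at that visit argues against scheduling it 8 days after injection 2. The stated window nonetheless allows it.

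**Conclusion.** The concern holds in a limited form. The protocol intends the sentinel Day 42 review to inform whether main-cohort second injections continue, and its calendar does not secure that order. The injection leads the completed review by R − L days nominally and by at most 7 + R − L days at the window limits. L and R are not in the documents, so no single value can be claimed. It would be wrong to say that the two events do fall on the same day: that is the earliest permitted case (L = 0 measured against Visit 5, or L = R measured against the completed review). It would also be wrong to treat 7 days as the expected reversal.

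The Visit 5 inconsistency rests on no assumption: 8 to 20 days after injection 2 under the stated windows, against the 14 days in the synopsis.

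Both matters bear on participant safety and are cheap to settle, so they should be corrected, with the weight tempered by the other safeguards and the small number of subjects concerned.

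**What to change.** Reconcile synopsis item 17 with sections 3.2, 4.12, 7.2.6 and 7.2.8 on two matters.

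1. The visit calendar and the stated purpose of the review should agree on whether main-cohort second injections follow the completed review, and the text should say what applies if the review is late.
2. The timing of Visit 5 should agree with the 14-day period after injection 2 that the synopsis, the diary and the solicited-event outcome assume.

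Which rule to adopt, and the clinical content of the review, remain with the sponsor and the DSMB. The cost is protocol wording and scheduling. Depending on what is decided, main enrolment might start a few days later.

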3.3. Blinded / randomized cohorts

After DSMB review and positive recommendation, sponsor will decide to continue the study by the enrollment of the remaining 84 participants (“Main Cohorts”), in a blinded randomized manner, in the low dose group (cohort A) or in high dose groups (cohort B and C).

Table 1: Treatment groups allocation

| Cohort | Treatment | Injection 1 D0 | Injection 2 D28 | Number of participants | | |
|--------|----------------------|-------------------|--------------------|------------------------------|------------------------------|---------|
| | | | | COVID-19 vaccine Sentinel | COVID-19 vaccine Main grp | Placebo |
| A | COVID-19 low Dosage | Vaccine | Vaccine | 3 | 21 | 6 |
| B | COVID-19 high Dosage | Vaccine | Vaccine | 3 | 21 | 6 |
| C | COVID-19 high Dosage | Vaccine | Placebo | 0 | 24 | 6 |

Participants will be observed closely for safety and immunogenicity from the first injection to the end of study.

The investigator, and site personnel performing study related assessments, all participants, as well as the sponsor’s representatives involved in the monitoring and conduct of the study will be blinded.

Only site personnel performing randomization, preparation of IMP and monitoring of the IMP handling process will be unblinded as well as the DSMB members (excluding observing DSMB members who will only have access to blinded safety report).

During the follow up phase (after all subjects have completed V6), the head of vaccine programs of Institut Pasteur and a project manager from the vaccine developer (Themis Bioscience GmbH a subsidiary of Merck & Co., Inc., Kenilworth, New Jersey USA,) will have access to the unblinded data for the purpose of immunogenicity assessment. In the current pandemic, rapid assessment of the potential of the vaccine, including the balance of safety and immunogenicity is required to move promising candidates forward as quickly as possible. All data will be stored on a secured server accessible with a login and password to which only the unblinded person has access. The risk of impact on the study is minimized as unblinding will occur when the treatment phase will have been completed, the analyses have been defined, and the unblinded personnel is not involved in the clinical evaluation and management of the participants.

3.4. Schematic overview of the study design

[figure not shown]

Figure 2: Schematic overview of the study design

3.5. Justification of doses

Multiple vaccines based on the same Measles Schwarz strain platform have undergone clinical evaluation and dose finding has repeatedly demonstrated that higher vaccine doses induce more robust neutralizing antibody responses (see for instance Reisinger et al 2018). The clinically most advanced candidate MV-CHIK has been administered to trial participants up to a dose of 1×10^6 TCID₅₀ per vaccination without any significant safety findings and has been well tolerated in pre-clinical repeated dose toxicity testing in NHPs up to 2.51×10^7 TCID₅₀ per dose. The selection of low and high dose used throughout this study was based on these findings.

4. STUDY POPULATION

4.1. Number of subjects

This study will be conducted in 90 healthy adults, who have fulfilled the following inclusion and exclusion criteria.

4.2. Inclusion criteria

The volunteer must fulfill the following criteria to be eligible for the study:

1. Males and females between the ages of 18 and 55 years (at the time of consent).
2. Healthy participant, according to the investigator's clinical judgment, as established by medical history, vital signs, physical examination, and laboratory assessments
3. Participant with a body mass index (BMI) <30.0 kg/m²
4. Provide written informed consent before initiation of any study procedures.
5. A female participant is eligible for this study if she is not pregnant given by a negative serum pregnancy test at screening and a negative urine pregnancy test at V1 (1st injection) or breast feeding and 1 of the following:
 - Of non-childbearing potential (i.e., women who have had a hysterectomy or tubal ligation or are postmenopausal, as defined by no menses in greater than or equal to 1 year).
 - Of childbearing potential but has been and agrees to continue practicing highly effective contraception or abstinence (if this is the preferred and usual lifestyle of the participant) from 30 days prior to vaccination up to 6 months after the last injection (D210).
 - Highly effective methods of contraception include 1 or more of the following:
 - male partner who is sterile (vasectomised) prior to the female participants entry into the study and is the sole sexual partner for the female participant;
 - hormonal (oral, intravaginal, transdermal, implantable or injectable);
 - an intrauterine hormone-releasing system (IUS);
 - an intrauterine device (IUD) with a documented failure rate of < 1%.
6. A female participant is eligible if she is willing to abstain from donating oocytes from the screening visit up to 6 months after the last injection (D210).
7. A male participant who is sexually active is eligible if he is willing to :
 - use a condom (with/without spermicidal product) from the screening visit up to 6 months after the last injection (D210) except if the male participant is sterile (e.g. vasectomised); the unique female sexual partner is postmenopausal (defined as no menses for 12 months without an alternative medical cause), is permanently sterilized (e.g. hysterectomy or tubal ligation), or use a highly effective methods of contraception;
 - not donate sperm from the screening visit up to 6 months after the last injection (D210);

- not plan to father a child from the screening visit up to 6 months after the last injection (D210).
8. Negative HIV 1/2 antibody/antigen test, Hepatitis B surface antigen (HBsAg), and Hepatitis C virus (HCV) antibody.
 9. Able to understand and comply with planned study procedures and willing to be available for all study-required procedures, visits and calls for the duration of the study.
 10. Willing to abstain from donating whole blood or blood derivatives, tissue or organ all along the study.
 11. Affiliated to a social security system, (except state medical aid) (Only for France).
 12. Volunteer registered in the French Health Ministry computerized file and authorized to participate in a clinical trial (only for France).

